# 3 Trial Design

## 3.1 Type/Design of Trial

This is a multicenter, randomized, double-blind, placebo- and active-controlled trial designed to assess the effect of brexpiprazole compared to placebo in adolescent subjects, ages 13 to 17 years at the time of informed consent/assent and at baseline (Day 1), with a *Diagnostic and Statistical Manual of Mental Disorders - Fifth Edition* (DSM-5) diagnosis of schizophrenia. The initial diagnosis of schizophrenia should be made by an adequately trained clinician (psychiatrist or local medical equivalent who is experienced in treating adolescents with schizophrenia). The diagnosis should then be confirmed by utilizing the Kiddie Schedule for Affective Disorders and Schizophrenia-Present and

Lifetime version (K-SADS-PL), performed by an adequately trained rater at the time of screening. The trial is planned to be conducted on an outpatient basis. Any hospitalization needed for prospective subjects, such as hospitalization needed to allow subjects to change medications in preparation for this trial requires discussion with the Medical Advisor.

This trial has a 6-week treatment double-blind period.

After a minimum 3-day washout period, subjects who continue to meet all entrance criteria (including Positive and Negative Syndrome Scale [PANSS] Total Score  $\geq$  80) at the baseline visit (Day 1) will be randomized 1:1:1 to 1 of 3 double-blind treatment arms:

- 2-4 mg brexpiprazole daily
- 10-20 mg aripiprazole daily
- Placebo

Brexpiprazole will be titrated to the minimum target dose of 2 mg in 8 days and aripiprazole will be titrated to the appropriate therapeutic dose consistent with the US package insert (minimum dose of 10 mg). Subjects who are unable to tolerate the minimum target dose will be discontinued. At the end of the titration period, investigators will be able to adjust the dose of double-blind IMP not to exceed 4 mg/day in the brexpiprazole treatment arm or 20 mg/day in the aripiprazole treatment arm. If subjects are not able to tolerate the minimum dose, they will be discontinued from the trial.

During the double-blind treatment phase, mandatory evaluations will take place at Day 1 (baseline), Day 4 (telephone call), and Weeks 1, 2, 3, 4, 5, and 6. However, at the discretion of the treating physician, more frequent evaluations are permitted. Data collected from subjects undergoing ad hoc evaluations may be excluded from efficacy analysis.

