### 3.4.2 Inclusion Criteria

Subjects are required at screening and baseline to meet the inclusion criteria presented in Table 3.4.2-1.

| Tabl | le 3.4.2-1 Inclusion Criteria   |
|------|---|
| 1.   | Written informed consent, assent, or both obtained from a legally acceptable representative (eg, guardian) or subject prior to the initiation of any protocol-required procedures. In addition, the subject must provide informed assent at screening and must be able to understand that he or she can withdraw from the trial at any time. All informed consent/assent procedures must be in accordance with the trial site's IRB/IEC and local regulatory requirements.  |
| 2.   | Male and female subjects 13 to 17 years of age, inclusive, at the time of informed consent/assent and at baseline (Day 1).  |
| 3.   | Subjects with a current primary diagnosis of schizophrenia, as defined by DSM-5 criteria and confirmed by the K-SADS-PL, and a history of the illness (diagnosis or symptoms) for at least 6 months prior to screening (as per subject, family, or healthcare provider, or by previous medical records). The initial diagnosis of schizophrenia must be made and documented initially by an adequately trained clinician (psychiatrist or local medical equivalent who is experienced in treating adolescents with schizophrenia), and the diagnosis should be confirmed afterwards by utilizing the K-SADS-PL performed by an adequately trained rater. (Subjects with a diagnosis of ADHD and treated with stimulants or other ADHD medications within 28 days are prohibited.) |
| 4.   | Subjects who, in the investigator's judgment, require treatment with antipsychotic medication(s).   |
| 5.   | Subjects with a PANSS Total Score $\geq$ 80 at screening and at baseline (Day 1).   |
| 6.   | Ability, in the opinion of the principal investigator, of the subject and the subject's legally acceptable representative (eg, guardian) or caregiver(s) to understand the nature of the trial and follow protocol requirements, including the prescribed dosage regimens, tablet ingestion, and discontinuation of prohibited concomitant medications, to read and understand the written word in order to complete subject-reported outcomes measures, and to be reliably rated on assessment scales.   |

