# 3.7.1.2 Baseline/Day 1 (Randomization)

If the subject is found to be eligible for the trial during the screening period, the subject will attend a baseline visit during which the following procedures will be completed prior to randomization:

- Inclusion/exclusion criteria will be verified. Review of inclusion/exclusion criteria at the baseline visit will be based on assessments performed during screening.
- Prior medications will be reviewed.
- A qualified and certified rater will administer the PANSS.
- A qualified rater will administer the CGAS.
- A qualified and certified rater will administer the CGI-S.
- The P-Q-LES-Q assessment will be completed by the subject.
- The investigator (or qualified designee) will complete the "Baseline/Screening" C-SSRS form.
- The investigator (or qualified designee) will administer the SAS, AIMS, and BARS.
- The investigator (or qualified designee) will administer the UKU and NY-AACENT.
- Body weight and waist circumference will be recorded.
  - Vital sign measurements (including blood pressure, body temperature, and pulse) will be recorded. Blood pressure and pulse are to be measured in the following order: supine, sitting, and standing after the subject has been in each position at least 3 minutes. Vital signs are to be completed before any blood is drawn.
- A standard 12-lead ECG will be performed predose after the subject has been supine and at rest for at least 5 minutes. The ECG is to be completed before any blood is drawn.
- Blood samples will be collected for clinical laboratory tests (hematology and serum chemistry [including blinded prolactin, HbA1c, and TSH]) after a minimum 8-hour fast, if fasting is possible. Vital sign and ECG assessments should be completed before any blood samples are collected.
- A urine pregnancy test will be performed predose for all females. The result must be negative prior to dosing.
- A serum pregnancy test will be collected for all females.
- Blood will be drawn for a plasma PK sample, which will be obtained 1–6 hours postdose, and the sampling time will be recorded.
- A pharmacogenomics (PGx) sample will be collected to determine the CYP2D6 metabolizer status.
- AEs and concomitant medications will be recorded.
- If the subject remains eligible for the trial after completion of the baseline evaluations, trial personnel will capture trial data within the eSource and randomize the subject to obtain an IMP assignment. The subject will receive the first dose of

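### Protocol 3.7.1.2 bases the baseline eligibility review on screening assessments, contradicting the Day 1 requirements stated elsewhere, including the Day 1 PANSS Total of at least 80

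*Protocol*

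**What the plan says.** The first procedure in Protocol 3.7.1.2 is to verify the inclusion and exclusion criteria. The checklist then says how: "Review of inclusion/exclusion criteria at the baseline visit will be based on assessments performed during screening". The sentence covers all criteria and carries no qualification.

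Other parts of the protocol tie eligibility to Day 1:

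- Section 3.4.2 opens with "Subjects are required at screening and baseline to meet the inclusion criteria presented in Table 3.4.2-1". Criterion 5 in that table sets the PANSS Total threshold at 80 and applies it both at screening and on Day 1.
- Section 3.1 describes the subjects to be randomized as follows: "After a minimum 3-day washout period, subjects who continue to meet all entrance criteria". It names the PANSS threshold and places the check at the baseline visit. The synopsis, Protocol 3.3.1 and SAP 3.1 and 3.3 repeat the Day 1 requirement.
- Section 3.7.1.2 introduces its list with "the subject will attend a baseline visit during which the following procedures will be completed prior to randomization", and the list includes "A qualified and certified rater will administer the PANSS". Its last bullet randomizes the subject only if eligibility still holds once the baseline evaluations are complete.

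**The concern.** A criterion that must hold on Day 1 cannot be checked on data collected up to 28 days earlier, or longer if the screening period is extended as Section 3.7.1.1 allows. The sentence in 3.7.1.2 is the only one in that checklist that says which data the review uses, and it names screening data. A coordinator working through the visit could therefore compare the screening PANSS with 80, mark the criterion as met, and then administer the Day 1 PANSS only as the baseline efficacy measure.

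Take a subject scoring 82 at screening and 74 on Day 1. The review sentence, read literally, finds this subject eligible. Criterion 5 and Section 3.1 find the same subject ineligible. At stake is whether the randomized population matches the stated one, and whether sites commit avoidable eligibility deviations because of an instruction in the protocol.

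**Working it through.** The plan states no figure on this point, so there is none to reproduce. The check sets the review sentence against each criterion that has a Day 1 element.

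1. **PANSS.** Criterion 5 needs a Day 1 value of at least 80. Table 3.7-1 schedules PANSS at screening and on Day 1, and 3.7.1.2 places the Day 1 rating before randomization. The score is produced at the visit, so nothing prevents its use. The review sentence conflicts with the criterion.
2. **C-SSRS.** Exclusion criterion 9 turns on Questions 4 and 5. Table 3.7-1 has no C-SSRS at screening, and Section 3.7.3.5.6 has the form completed at the baseline visit to decide eligibility. Under the protocol there is no screening C-SSRS to review. (SAP 10.11 describes the eligibility form as completed at screening. That differs from the protocol's schedule and should be reconciled at the same time.)
3. **ECG.** Section 3.7.3.4 notes that the central read of the baseline ECG will not be back in time, and randomizes on the screening central read together with the baseline site read. Even here, where the reason for relying on screening is explicit, the protocol uses a Day 1 result. The review sentence leaves it out.
4. **Urine pregnancy test.** 3.7.1.2 and Section 3.7.3.2 require a negative Day 1 result before dosing. This is again a Day 1 decision.
5. **Vital signs.** Exclusion criterion 13 concerns blood pressure. Vital signs are measured on Day 1 before randomization, and Section 3.4.3 applies the exclusions at screening and baseline.
6. **Assessments at screening only.** K-SADS-PL, the physical examination and the urine drug screen are scheduled at screening and not on Day 1. For these the review sentence is correct, and a rewording must keep it so.

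Downstream handling:

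- Protocol 7.2 and SAP 5.4 define the Efficacy Sample by randomization, at least one dose, a baseline PANSS and at least one postbaseline PANSS. A baseline PANSS of at least 80 is not a condition, and no per-protocol set is defined.
- The documents describe no mandatory check of the Day 1 PANSS at the point of IWRS assignment. Section 3.7.1.1 only reserves the sponsor's right to external oversight of severity and other selection factors.
- A subject randomized in error, dosed, and rated on PANSS after baseline therefore remains in the primary MMRM.

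**The case against.** The strongest reply is that the protocol as a whole is clear. Criterion 5 is explicit, the Day 1 requirement recurs in the synopsis, Sections 3.1 and 3.3.1 and the SAP, and the last bullet of 3.7.1.2 bars a subject who is no longer eligible. Section 3.13 lists enrolment against eligibility criteria among significant deviations that require contact with the sponsor. The review sentence may be meant only for results not yet back on Day 1. Most of this stands. A reader might infer that the protocol permits a subject below 80 on Day 1 to be randomized. It does not. What remains is that the sentence states no such limit, and the closing bullet does not say on which data eligibility is judged.

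A reader might also try to put a number on it. Assume a bivariate normal with mean 90 to 100, SD 10 to 14, correlation 0.7 to 0.9 and no mean shift between visits. Then 1.0% to 12.7% of those at or above 80 at screening fall below 80 on Day 1. Applied to 315 subjects, 315 × 0.010 ≈ 3 and 315 × 0.127 ≈ 40. This is not an estimate of the number affected. Every input is assumed, and it requires every site to ignore criterion 5, Section 3.1 and the closing bullet. The direction of any shift is also unknown, because subjects wash out antipsychotics during screening. If scores worsened by an assumed 5 points, the same model gives 0.1% to 5.8%.

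Finally, a reader might infer that such subjects bring a regressed baseline and weaken separation from placebo. The documents do not support this. SAP 7.2 takes the last pre-dose value as baseline, and the MMRM adjusts for baseline and baseline by visit. In the same assumed model with a third rating and no treatment effect, selection on screening alone gives a mean change from Day 1 of about 0. Selection on both ratings gives about −0.04 to −1.2 points. It is the second threshold that induces regression in the change score. With 30 items scored from 1, the PANSS minimum is 30, so a Day 1 score of 74 still leaves 74 − 30 = 44 points of room against a target difference of 7.4.

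**Conclusion.** The concern holds as an internal contradiction in an operational instruction. The review sentence in 3.7.1.2 conflicts with criterion 5, Sections 3.1, 3.7.3.4 and 3.7.3.5.6, and the last bullet of its own section, and these passages must be reconciled. The consequence is a risk of avoidable eligibility deviations at sites that follow the sentence literally. It is not a gap in the eligibility rule.

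The size cannot be derived: the documents give neither a distribution of PANSS at entry nor any indication of how sites read the sentence. The planned 105 subjects per arm, the stated power, the endpoint and the analysis model are unaffected. The point is worth correcting because the sentence sits on the checklist used on the day of randomization, and nothing later in the analysis plan would remove a subject entered in error.

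**What to change.** Reword the one bullet in Protocol 3.7.1.2 along these lines:

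- Criteria with a Day 1 requirement, or with a Day 1 assessment available before randomization, are verified on Day 1 data. These are PANSS Total per criterion 5, C-SSRS, vital signs, the site-read ECG and the urine pregnancy test.
- Screening results are used for assessments done only at screening, such as K-SADS-PL, physical examination and urine drug screen, and for central laboratory or central ECG results not available before randomization.

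The second part matters. Limiting screening data to pending central results alone would leave the diagnosis and drug-screen criteria with no usable evidence at baseline.

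The cost is one bullet in an amendment or a site clarification. It adds no assessment and no new threshold, because the Day 1 PANSS is already done before randomization and criterion 5 already sets the cut-off. For subjects already randomized, the sponsor can list those with a baseline PANSS Total below 80 from data already collected and report them as eligibility deviations. That would also supply the count that the documents cannot.

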# 3.7.1.5 Week 6 (End of Treatment)

The treatment period will conclude at the Week 6 visit. Subjects will take the last dose of IMP either prior to the Week 6 visit on the same calendar day or during the Week 6 visit whenever possible, depending on the time of day when the subject typically takes the IMP relative to the scheduled time for the visit. The following activities and assessments will occur at Week 6/end of treatment:

- Trial personnel will register completion or discontinuation from the trial in eSource.
- A qualified and certified rater will administer the PANSS.
- A qualified rater will administer the CGAS.
- A qualified and certified rater will administer the CGI-S.
- A qualified and certified rater will administer the CGI-I.
- The P-Q-LES-Q assessment will be completed by the subject.
- The investigator (or qualified designee) will complete the "Since Last Visit" C-SSRS form.
- The investigator (or qualified designee) will administer the SAS, AIMS, and BARS.
- The investigator (or qualified designee) will administer the UKU and NY-AACENT.
- The investigator (or qualified designee) will complete Tanner Staging assessment.
- A physical examination will be performed.
- Body weight, height, and waist circumference will be recorded.
  - Vital sign measurements (including blood pressure, body temperature, and pulse) will be recorded. Blood pressure and pulse are to be measured in the following order: supine, sitting, and standing after the subject has been in each position at least 3 minutes. Vital signs are to be completed before any blood is drawn.
- A standard 12-lead ECG will be performed postdose after the subject has been supine and at rest for at least 5 minutes. The ECG is to be completed before any blood is drawn.
- Blood samples will be collected for clinical laboratory tests (hematology and serum chemistry [including blinded prolactin, HbA1c, and TSH]) after a minimum 8-hour fast, if fasting is possible. Vital sign and ECG assessments should be completed before any blood samples are collected.
- A urine pregnancy test will be performed predose for all females.
- A serum pregnancy test will be performed for all females.

- Urine will be collected from all potential subjects for urinalysis and urine screen(s) for drugs of abuse.
- A plasma PK sample will be obtained within 1-6 hours postdose when possible. The time of each PK sample as well as the time of the last 3 doses of IMP will be recorded.
- Drug accountability.
- AEs and concomitant medications will be recorded.

Eligible subjects who complete this 6-week trial will have the option to enroll into an open-label safety trial of brexpiprazole (Protocol 331-10-236). If subjects are not able to tolerate the assigned dose or the decreased dose, or have no improvement in schizophrenia symptoms, they will be discontinued from the trial.

# 3.7.1.6 Early Termination

If a subject discontinues early before Week 6, procedures noted for Week 6 must be completed at the ET visit. Attempts should be made to complete all evaluations, particularly efficacy assessments (ie, PANSS, CGAS, CGI-S, and CGI-I), prior to the administration of any new psychotropic medications. However, if the subject receives a new antipsychotic prior to ET procedures, no efficacy assessments should be done. Any prohibited medications started before the end of the trial assessments should be documented as a protocol deviation.

# 3.7.1.7 Follow-Up

All subjects who do not enroll in the open-label rollover trial (Protocol 331-10-236) will be followed up by a telephone assessment 21 ( $\pm$  2) days after the last dose of IMP to assess any new or ongoing AEs and to record any concomitant medications.

#### 3.7.2 Efficacy Assessments

It is required that a qualified and experienced clinician administer the efficacy assessments (ie, PANSS, CGAS, CGI-S, and CGI-I). Raters will be trained on the administration of these scales and, in addition, must be certified for this trial to administer the PANSS. The number of raters within each trial site should be kept to a minimum. All efforts will be made to ensure that the same clinician administers the scales for a given subject. Notations in the subject's trial records should substantiate the ratings. Training, certification, and materials for rating will be provided. The P-Q-LES-Q (a subject-rated scale) will be collected as specified in the protocol. Instructions on how to complete the form are contained at the top of the scale (Appendix 9).

# 3.7.2.1 Positive and Negative Syndrome Scale

The PANSS consists of 3 subscales containing a total of 30 symptom constructs. For each symptom construct, severity is rated on a 7-point scale, with a score of 1 indicating the absence of symptoms and a score of 7 indicating extremely severe symptoms. The symptom constructs for each subscale are as follows:

- Positive Subscale (7 positive symptom constructs: delusions, conceptual disorganization, hallucinatory behavior, excitement, grandiosity, suspiciousness/persecution, and hostility),
- Negative Subscale (7 negative symptom constructs: blunted affect, emotional withdrawal, poor rapport, passive/apathetic social withdrawal, difficulty in abstract thinking, lack of spontaneity and conversation flow, stereotyped thinking), and
- 3) General Psychopathology Subscale (16 symptom constructs: somatic concern, anxiety, guilt feelings, tension, mannerisms and posturing, depression, motor retardation, uncooperativeness, unusual thought content, disorientation, poor attention, lack of judgment and insight, disturbance of volition, poor impulse control, preoccupation, and active social avoidance).

A copy of the PANSS is provided in Appendix 5.

# 3.7.2.2 Children's Global Assessment Scale

The CGAS is a 100-point rating scale measuring psychological, social and school functioning for children aged 6-17. It was adapted from the Adult Global Assessment Scale (GAS). The GAS is a rating scale for evaluating the overall functioning of a subject during a specified time period on a continuum from psychological or psychiatric sickness to health. The CGAS is a valid and reliable tool for rating a child's general level of functioning on a health-illness continuum. The CGAS was developed by Schaffer and colleagues to provide a global measure of severity of disturbance in children and adolescent. Notation in the subject's trial records should substantiate the ratings. A copy of the CGAS is provided in Appendix 6.

# 3.7.2.3 Clinical Global Impression - Severity of Illness Scale

The severity of illness for each subject will be rated using the CGI-S. To perform this assessment, the rater or investigator will answer the following question: "Considering your total clinical experience with this particular population, how mentally ill is the patient at this time?" Response choices include: 0 = not assessed; 1 = normal, not at all ill; 2 = borderline mentally ill; 3 = mildly ill; 4 = moderately ill; 5 = markedly ill; 6 = severely ill; and 7 = among the most extremely ill patients. A sample of the CGI-S is provided in Appendix 7.

#### 3.7.2.4 Clinical Global Impression - Improvement Scale

The efficacy of IMP will be rated for each subject using the CGI-I. The rater or investigator will rate the subject's total improvement whether or not it is due entirely to drug treatment. All responses will be compared to the subject's condition at baseline prior to the first dose of double-blind IMP. Response choices include: 0 = not assessed, 1 = very much improved, 2 = much improved, 3 = minimally improved, 4 = no change, 5 = minimally worse, 6 = much worse, and 7 = very much worse. A sample of the CGI-I is provided in Appendix 8.

### 3.7.3 Safety Assessments

#### 3.7.3.1 Adverse Events

Refer to Section 5, Reporting of Adverse Events.

#### 3.7.3.2 Clinical Laboratory Assessments

A central laboratory designated by the sponsor will be used for all laboratory testing required during the trial. The central laboratory should be used for all laboratory testing whenever possible (including unscheduled and follow-up laboratory tests, if needed). In cases where an immediate result is required for a particular laboratory test, the sample should be divided and sent to both a local laboratory and the designated central laboratory. Urine will be collected and blood will be drawn from each subject during screening prior to treatment with IMP and then at the scheduled visits designated in Table 3.7-1. The results of these tests must be reviewed by the investigator prior to initiation of IMP. Additional urine and blood samples may be collected for further evaluation of safety as warranted by the investigator's judgment. Subjects must be fasting for a minimum of 8 hours prior to blood draws for screening laboratory assessments, if at all possible. If fasting blood samples are not feasible at screening, nonfasting blood samples may be obtained initially for determining eligibility for the trial. If a subject is not fasting at a visit, the blood draw should still be performed and the status documented as nonfasting on the laboratory requisition sheet. The central laboratory will provide laboratory results to the sponsor electronically.

| Table 3.7.3.2-1Clinical Laboratory Assessments |  |  |  |  |
|--|--|--|--|--|
| Hematology:                                    | Serum Chemistry:   |  |  |  |
| Hematocrit                                     | Alkaline Phosphatase (ALP)                                 |  |  |  |
| Hemoglobin                                     | Alanine Aminotransferase (ALT)                             |  |  |  |
| Mean Corpuscular Hemoglobin Concentration      | Aspartate Aminotransferase (AST)                           |  |  |  |
| Mean Corpuscular Volume                        | Bilirubin, total   |  |  |  |
| Platelets                                      | Blood Urea Nitrogen (BUN)                                  |  |  |  |
| Red Blood Cell (RBC) count                     | Calcium  |  |  |  |
| White Blood Cell (WBC) count with differential | Chloride   |  |  |  |
|  | Cholesterol (total, LDL, and HDL)                          |  |  |  |
| Urinalysis:                                    | СРК  |  |  |  |
| Appearance                                     | Creatinine   |  |  |  |
| Color  | Gamma Glutamyl Transferase (GGT)                           |  |  |  |
| Blood  | Glucose  |  |  |  |
| Glucose  | Lactic Dehydrogenase (LDH)                                 |  |  |  |
| Microscopic analysis, WBC/RBC counts per high  | Potassium  |  |  |  |
| powered field                                  | Prolactin a                                     |  |  |  |
| pH   | Protein, total   |  |  |  |
| Protein  | Sodium   |  |  |  |
| Specific gravity                               | Triglycerides  |  |  |  |
|  | Uric acid  |  |  |  |
|  |  |  |  |  |
|  | Additional Tests:  |  |  |  |
|  | Urine (or serum) pregnancy for all females                 |  |  |  |
|  | TSH, with reflex to free T 4 if TSH is abnormal |  |  |  |
|  | HbA1c  |  |  |  |

HDL = high-density lipoprotein; LDL = low-density lipoprotein aResults blinded.

No more than 24.5 mL of blood will be taken at each visit designated in Table 3.7-1 for the purposes of clinical laboratory assessments, serum pregnancy tests, PK and PGx analyses. The laboratory tests to be evaluated in this trial are listed in Table 3.7.3.2-1.

A pregnancy test will be conducted in all females prior to trial intervention; results must be available prior to the administration of the IMP. Subjects with a positive serum test result at screening will be excluded from the trial. A urine pregnancy test will be collected at screening and predose on Day 1, Week 6, and ET. The urine pregnancy test must be negative prior to dosing on Day 1. The frequency of pregnancy tests may be modified based on local regulatory requirements. Additional urine or serum pregnancy testing may be done at the discretion of the investigator.

Any value outside the normal range will be flagged for the attention of the investigator, who must indicate whether or not a flagged value is of clinical significance. If one or more values are questionable, the test(s) may be repeated. If the result of any test (or repeat test, if done) is indicated as clinically significant in the samples taken during the screening period, the subject will NOT be enrolled into the trial without the permission of

55

the medical monitor. In addition, follow-up unscheduled laboratory tests should be performed on clinically significant abnormalities. Unscheduled laboratory tests may be repeated at any time at the discretion of the investigator for appropriate medical care.

The following laboratory test results are exclusionary:

- 1) Platelets  $\leq 75000/\text{mm}^3$
- 2) Hemoglobin  $\leq 11 \text{ g/dL}$
- 3) Neutrophils, absolute  $\leq 1000/\text{mm}^3$
- 4) WBC count  $\leq 2800/\text{mm}^3$
- 5) Aspartate aminotransferase (AST)  $> 3 \times$  the upper limit of normal (ULN)
- 6) Alanine aminotransferase  $(ALT) > 3 \times \text{the ULN}$
- 7) Creatinine  $\geq 2 \text{ mg/dL}$
- 8) HbA1c  $\ge$  7.0%
- 9) Creatine phosphokinase (CPK) > 3 × ULN
- Abnormal free T4, unless discussed with and approved by Medical Advisor. (Note: Free T4 is measured only if result for TSH is abnormal.)
- 11) QTcF or QTcN  $\geq$  450 msec for males and  $\geq$  470 msec for females

In addition, subjects should be excluded if they have any other abnormal laboratory test result at screening that, in the investigator's judgment, is medically significant in that it would impact the safety of the subject or the interpretation of the trial results. However, any abnormal screening laboratory result(s) considered to be clinically significant should be repeated as soon as possible to confirm the finding(s) before excluding the subject from the trial.

Appendix 2 is included to assist investigators in their assessments of results that may be potentially medically relevant, depending on the subject's medical history and clinical presentation.

